Prior to discharge from the procedure, the research staff shall review study requirements with the subject to help ensure compliance with the follow-up schedule. Telephone numbers will be obtained from the participant at the time of informed consent to ensure the clinic is able to contact the subject and primary physician as needed. Patients will be instructed on post-procedural wound care and limitation of certain physical activities. Antibiotics and pain medication may be prescribed at the discretion of the investigator.

2-4-8 Randomization and Blinding

Randomization assignments will be generated by a software program using randomization with a 1:1 allocation to sensory or subsensory activation. After production of the allocation sequence, the sequence will be locked, password protected and placed in an online file storage system by the staff who produced it. The Field Clinical Engineer is the only study personnel who can view the randomization sequence prior to unblinding.

Both the principal investigator and patient will be blinded to the patient's treatment assignment until completion of the primary endpoint visit at 3 months post-activation. The FCE will be unblinded to the participant's treatment assignment, allowing them to activate the patient to their treatment level.

Randomization will occur on the day of the activation and after all baseline data have been collected, eligibility has been confirmed and the device has been implanted. On the day of the activation, the FCE will check the allocation sequence.

Until the primary endpoint is reached, subjects will be required to remain in their randomized treatment arm and not undergo reprogramming. If the subject reports that the stimulation in their current treatment arm is uncomfortable and requests reprogramming, a protocol deviation will be required, and the patient may not be considered in the primary analysis population.

Before the primary endpoint at 3 months post activation, unblinding of participants will only occur when medically necessary. In the event of a device- or procedure- related SAE or device malfunction, the sponsor may authorize unblinding of the physician and the participant in order to adequately assess the event.

2-4-9 eCoin Activation

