All subjects will return for a device activation visit approximately four weeks after implantation. At this point, the follow-up visit clock will start to run (that is, the follow-up visits will be characterized in relationship to the date of the activation visit).

The subject will be provided with a 3-day voiding diary to complete in the 7 days prior to the next visits (occurring 2 and 3 months post-activation). At least 3 days prior to the next visit, a member of the study staff will telephone subjects to remind them that they should begin the 3-day diary.

2-4-10 Establishment of the Amplitude Setting in each Treatment Arm

Amplitude level ranges in practice from 0.5 to 15 mA. Sensory threshold is defined as the lowest amplitude where the subject first perceives sensation of the stimulation in the foot, heel, toes or eCoin device site while in a prone, seated and standing position.

Subjects will be informed that they may periodically feel a tingling or notice a muscle twitch. In particular, subjects may feel a motor response (flexing of the big toe and/or fanning of the other toes) and sensory response (a radiating sensation may be felt at the sole of the foot and in the toes). Typical descriptions of tibial nerve stimulation sensation include feeling a 'buzzing', 'tingling' and 'vibrating' sensation.

2-4-10-1 Sensory Treatment Arm Activation Protocol

The subject's sensory threshold is determined by turning the device on to 0.5 mA and increasing the amplitude by one level until the subject reports sensation. If the subject does not feel sensation at any amplitude, they will be set at 8 mA, this will be considered a deviation to the protocol.

2-4-10-2 Subsensory Treatment Arm Activation Protocol

The subject's sensory threshold is determined by turning the device on to 0.5 mA and increasing the amplitude by one level until the subject first reports sensation. Once the first sensory threshold is determined, the set amplitude will be lowered to approximately 75% of the sensory threshold, accounting for rounding. Patients who do not have sensory at the highest amplitude will be set at 11mA. See the below table for sensory threshold and level set correlations:

Sensory Threshold	Level Set
0.5 mA	Protocol Deviation, set 0.5 mA
1 mA	0.5 mA
2 mA	1 mA
3 mA	2 mA
4 mA	3 mA
5 mA	4 mA
6 mA	5 mA
7 mA	5 mA
8 mA	6 mA
9 mA	7 mA
10 mA	8 mA
11 mA	8 mA
12 mA	9 mA
13 mA	10 mA
14 mA	11 mA
15 mA	11 mA
No sensation	11 mA

2-4-11 Post Activation Follow-up Procedure

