### 5.3. Randomization and Blinding

Randomization assignments will be generated by the software program Sealed Envelope Ltd. 2022 using block randomization with variable block sizes of 2, 4, and 6. No stratification will be used. Randomization assignments will be generated for 50 subjects. After production of the allocation sequence, the sequence will be locked, password protected and placed in an online file storage system by the Clinical Trial Manager or staff who produced it. The Investigator and Patient must not view the randomization sequence prior to unblinding, unless there are extenuating circumstances described below.

Both the principal investigator (including site study staff) and patient will be blinded to the patient's treatment assignment until completion of the primary endpoint visit at 3 months post-activation. The FCE will be unblinded to the participant's treatment assignment, allowing them to activate the patient to their treatment level. The blinding technique is described in detail in the ESSENCE Blinding Work Procedure document.

Treatment assignment will occur on the day of the activation and after all baseline data has been collected, eligibility has been confirmed and the device has been implanted. On the day of the activation, the FCE will check the central allocation sequence and program the patient accordingly.

Until the primary endpoint is reached, subjects will be required to remain in their assigned treatment arm and not undergo reprogramming that is a departure from their assigned treatment group. If the subject reports that the stimulation in their current treatment arm is uncomfortable and requests reprogramming, a protocol deviation will be required, and the patient may not be considered in the primary analysis population.

If unblinding has occurred, the circumstances around the unblinding must be documented on an unblinding CRF and the Sponsor notified as soon as possible.

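### As written, the unblinded field engineer can know the arm while eliciting the sensory threshold, and that reading sets the amplitude and can decide per-protocol membership

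*Protocol*

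**What the plan says.** - **Access.** Protocol 2-4-8: "After production of the allocation sequence, the sequence will be locked, password protected and placed in an online file storage system", and "The Field Clinical Engineer is the only study personnel who can view the randomization sequence prior to unblinding". SAP 5.3 adds that "Randomization assignments will be generated for 50 subjects", "using block randomization with variable block sizes of 2, 4, and 6. No stratification will be used". Neither document describes releasing assignments one at a time.
- **Activation day.** SAP 5.3: "On the day of the activation, the FCE will check the central allocation sequence and program the patient accordingly". Protocol 2-3-3-1 makes the sponsor's FCEs responsible for carrying out the activation protocol and setting the amplitude.
- **Threshold.** Protocol 2-4-10 gives one shared definition of sensory threshold. The elicitation is then written twice, once inside each arm's activation steps (2-4-10-1 and 2-4-10-2), in nearly the same words: start at 0.5 mA and continue "increasing the amplitude by one level until the subject first reports sensation" (the subsensory version).
- **Use of the reading.** It fixes the set amplitude: the first-felt level in the sensory arm (Protocol 2-3-1), and a tabulated level of roughly three quarters of the threshold in the subsensory arm (2-4-10-2). It also decides two exclusions from the per-protocol population, which is the primary population: no sensation at any level (sensory arm only) and sensation at 0.5 mA (subsensory arm only). See Protocol 2-6-4-2 and SAP 9.6.
- **Safeguards.** Under Protocol 2-4-8, randomization comes after baseline data, eligibility confirmation and implantation, and the subject and investigator are blinded to 3 months. SAP 10.3 repeats the efficacy analyses in the ITT population. SAP 5.3 refers to a separate Blinding Work Procedure, which is not among the documents.

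**The concern.** The threshold is a subjective reading. The FCE conducts the test and is also the one person at the visit allowed to know the arm. An operator who knows the arm can, without intending to, step faster or slower, prompt differently, or treat a doubtful report differently across the three body positions in the definition.

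Two things depend on the result. One is the contrast under study: if subsensory subjects are set at their true threshold, the arms differ less than intended. The other is who is counted in the primary analysis, because the excluding readings differ by arm. The two exposures differ in how far they can be repaired: an exclusion can be reversed in a second analysis set, but a delivered amplitude cannot.

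**Working it through.** **1. The plan's own allowance.** The sample size sections (Protocol 2-6-5, SAP 6) take the pivotal-trial proportions (n = 130) and halve them, because each scenario affects one arm:
- threshold of 0.5 mA: 3.85% / 2 = 1.9%, stated as 0.02;
- threshold not identified: 6.15% / 2 = 3.1%, stated as 0.03;
- with 10% dropout: 0.02 + 0.03 + 0.10 = 0.15, the plan's 15% per-protocol loss.

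These figures reproduce and are not in dispute.

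**2. Subjects at the excluding readings.** Take 40 subjects at 1:1, so 20 per arm:
- sensory arm, no sensation: 20 × 0.0615 = 1.23 expected; chance of at least one = 1 − (1 − 8/130)^20 = 72%;
- subsensory arm, 0.5 mA: 20 × 0.0385 = 0.77 expected; chance of at least one = 1 − (1 − 5/130)^20 = 54%.

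**3. Effect of a one-level error on the subsensory amplitude.** From the table in Protocol 2-4-10-2, with the threshold recorded one level too high:

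| True threshold (mA) | Recorded as | Level set | Level set on a correct reading |
|---|---|---|---|
| 0.5 | 1 | 0.5 | 0.5 (deviation) |
| 1 | 2 | 1 | 0.5 |
| 2 | 3 | 2 | 1 |
| 3 | 4 | 3 | 2 |
| 4 | 5 | 4 | 3 |
| 5 | 6 | 5 | 4 |
| 6 | 7 | 5 | 5 |
| 7 | 8 | 6 | 5 |

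For true thresholds of 1 to 5 mA, the set level lands on the true threshold, so the subject is in effect programmed at sensory level. From 6 mA upward, a one-level error leaves the set level below the true threshold throughout the table. At 0.5 mA the level does not change, but recording 1 mA keeps the subject in the per-protocol set.

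Not every error matters. The table has 17 rows and so 16 adjacent pairs. Five pairs share a set level: 0.5/1, 6/7, 10/11, 14/15 and 15/no sensation. The other 11 differ.

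**4. Order of steps.** Protocol 2-4-8 says only that the FCE checks the sequence on the day. SAP 5.3 says check, then program. The elicitation steps sit under arm-specific headings. Read together, these allow the arm to be known first, and they suggest it. They do not state the order, and no sentence requires the threshold to be recorded first.

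**The case against.** The case on the other side is substantial.

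- **The reading comes from a blinded subject, through a step-up procedure worded almost identically for both arms.** This stands and limits the risk. What remains is influence through pacing, prompting and recording, which the documents do not control.
- **The lookup may already follow the threshold, and access may already be restricted.** The Blinding Work Procedure could say so. A reader might infer from the Protocol that every future assignment is known to the FCE with certainty. That is the plain reading of the access sentence, but without the procedure it cannot be asserted as fact.
- **Enrolment is protected.** A reader might infer a classic failure of allocation concealment. The documents do not support that: eligibility, baseline data and implantation all precede randomization, and the FCE has no stated part in enrolment.
- **Visit order.** A reader might also infer that the FCE could arrange activations to suit the list. No section gives the FCE a scheduling role. Protocol 2-4-13 gives appointment compliance to site coordinators, and 2-4-2 ties activation to 23 to 43 days after implant.
- **ITT repeat.** The ITT definition in SAP 7.2 has no threshold exclusion, so SAP 10.3 restores subjects removed on that ground. This stands for membership. It does not help with an amplitude set from a biased reading.
- **The study is descriptive, with no powered comparison of arms (SAP 5.1).** True, and it limits the weight of the point. The per-arm summaries still need each arm to have received its intended programming.

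**Conclusion.** The point holds as a preventable exposure at one step. The documents allow an operator who knows the arm to elicit and record the reading that sets the amplitude and triggers arm-specific exclusion from the primary set.

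Its size is modest. A one-level over-reading removes the subsensory margin for true thresholds of 1 to 5 mA; how many subjects fall in that range is not given. About 1.2 sensory and 0.8 subsensory subjects are expected at the excluding readings, assuming 20 per arm and pivotal-trial rates. A reader might take those two figures as the number misclassified. They are the expected number truly at those readings, and nothing in the documents allows an estimate of bias in the change in incontinence episodes. Nor do the documents say that the FCE adjudicates per-protocol membership; the threshold result does that.

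The conclusion assumes that the unseen Blinding Work Procedure does not already fix the order of steps. If it does, the remaining task is to say so in the Protocol and SAP.

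**What to change.** In Protocol 2-4-8 and 2-4-10 and in SAP 5.3, and consistently in the Blinding Work Procedure:

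1. State the step-up elicitation once, in 2-4-10, as common to both arms.
2. Require the FCE to record the threshold (or that none was found) with a time stamp before opening the assignment.
3. Open only that subject's assignment, for example through the randomization software or a single-subject sealed file. The FCE has no access to the full list.
4. Program according to the arm, as now.

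No amplitude rule, visit or sample size changes. The cost is one case report form field, a few minutes at each activation, and one-off set-up of single-assignment release for up to 10 sites.

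While these sections are open, reconcile Protocol 2-7-6-2 with 2-6-4-2 and SAP 9.6. The first lists the two threshold findings as examples of minor deviations, a class defined as having no bearing on scientific validity. The other two treat them as departures significant enough to remove a subject from the primary population.

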eCoin is the first fully implantable tibial neurostimulator to be approved by FDA for treatment of urgency urinary incontinence. The eCoin device is a leadless, coin-sized neurostimulator composed of radially symmetric material lining the rim and bottom center. It emits a dome-shaped electrical field to deliver low-

Valencia Technologies Corporation

duty cycle stimulation to the tibial nerve. The device is to be implanted under local anesthetic in the lower leg, and once activated delivers automatic 30-minute treatment sessions without the need for patient management. This study will explore through a standard randomized controlled trial two different amplitude settings that achieve a reduction in UUI episodes, with the goal of gathering information to optimize device programming..

1-3-1 Manufacturer name, address, and contact information

Name of device manufacturer: Valencia Technologies Corporation

Address: [name]

Contact Person: [name], Chief Executive Officer

[contact]

[contact]

1-4 Indication for Use

The eCoin Peripheral Neurostimulator is intended to be used to treat urgency urinary incontinence in patients intolerant to or having an inadequate response to other more conservative treatments or who have undergone a successful trial of percutaneous tibial nerve stimulation. These indications are approved under P200036.

1-4-1 Contraindications

The eCoin Peripheral Neurostimulator is contraindicated for the following patients:

- Poor Surgical Candidates: The eCoin should not be implanted in patients who are poor surgical candidates. Poor surgical candidates include those who have:
 - Open wounds or sores on the lower leg or foot
 - Had prior surgery in the implant area
 - Had previous, unhealed trauma in the implant area
 - Pitting edema ($\geq 2+$) in the lower leg
 - Venous disease/insufficiency in the lower leg
 - Arterial disease/insufficiency in the lower leg
 - Vasculitis or dermatologic conditions in the lower leg
 - Infections near the implantation site in the lower leg
- Patient can not properly operate the Patient Controller Magnets and paper tape for use in the event of unintended or unwanted stimulation.

1-5 Prior Studies of the Valencia eCoin System

Three clinical studies have been conducted that document the safety and efficacy of eCoin in the treatment of UUI (179 unique patients implanted).

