The eCoin system was tested in a prospective, multicenter feasibility study on 46 subjects in the United States and New Zealand, in a second study that invited 23 feasibility subjects to receive a replacement device, and in a prospective multicenter pivotal study on 133 subjects in the United States.

111-6133	Clinical Study Protocol ESSENCE	Rev: 1	Date Printed:4/10/2025	Page 10 of 38
----------	---------------------------------	--------	------------------------	---------------

The overall findings from the 3 separate studies assessing eCoin's efficacy in UUI treatment have proven safety and effectiveness. In the feasibility trial, the responder rate at 12 months was 65%; in the follow-on study, the responder rate at 6 months was 82%; and the responder rate in the pivotal trial after 48 weeks was 68%. In each study, other diary assessments show improvement as well, with analyses demonstrating consistent improvement in urinary voids, urgency episodes and nocturia across all timepoints, as well as clinically meaningful improvements in patient reported outcomes.

The eCoin device and associated procedure caused minimal adverse events, especially events resulting in changes of amplitude, or need for concomitant medication, serious adverse events, events resulting in withdrawal, and deaths. As usual for neuromodulation, infection, stimulation discomfort, and migration are the key related adverse events—all occurring at low-normal rates. The device is implanted in a 20-minute office or outpatient procedure under local anesthetic. The eCoin had a low rate of related adverse events. Combined with showing a positive benefit in patients with UUI, the benefits of the eCoin outweigh the risks of the device and procedure.

Results from the pivotal trial were leveraged in the original premarket approval application (PMA) P200036. The eCoin device was approved by the FDA on March 1, 2022. There are two on-going clinical trials that continue to assess the safety and efficacy of the eCoin device.

2 Investigational Plan

2-1 Purpose

This investigation is designed as a double-blinded, randomized controlled study assessing the effect of programming at and below sensory level with the Valencia Technologies eCoin system.

The objective of this study is to evaluate the effect of these two programming methodologies (setting amplitudes at sensory vs. subsensory levels) on urgency urinary incontinence symptoms, quality of life, and patient satisfaction.

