For the visit involving a 3-day diary, the diary should be completed over 3 consecutive days during the 7 days prior to the indicated visit

- Visit 1: Screening Procedures (informed consent, demographic and medical history and concomitant medication/therapy information, physical examination, and vital signs are collected, subjects begin 2 week wash-off of OAB medications or 4 week wash-off of PTNS if applicable, eligibility determination)
- Visit 2: Baseline Assessments (3-day voiding diary, OABq, patient satisfaction survey, concomitant therapy review, final eligibility determination) (Time: Between 3 and 32 days from Visit 1)
- Visit 3: Implant Procedure (vital signs collected, adverse event assessment, concomitant therapy review, pictures taken) (Time: Between 0 and 20 days from Visit 2)
- Visit 4: Incision Healing Check (vital signs collected, adverse event assessment, pictures taken, concomitant therapy review) (Time: Between 9 and 19 days from Visit 3)
- Visit 5: Initial Activation and Randomization at Sensory or Subsensory (vitals signs collected, adverse event assessment, pictures taken, concomitant therapy review) (Field Clinical Engineer present) (Time: Between 23 and 43 days from Visit 3)
- Visit 6 (2 months post-activation): Follow-up assessments (3-day voiding diary, OABq, patient satisfaction survey, adverse event assessments, concomitant medication therapy review) (Time: Between 7 and 9 weeks from Visit 5)
- Visit 7 (3 months post-activation): Follow-up assessments (3-day voiding diary, OABq, patient satisfaction survey, adverse event assessments, concomitant medication therapy review, unblinding and reprogramming as requested (Field Clinical Engineer present)) (Time: Between 12 and 14 weeks from Visit 5)
- Visit 8 (4 months post-activation): Follow-up assessments (3-day voiding diary, OABq, end of study survey, adverse event assessments, concomitant medication therapy review) (Time: Between 16 and 18 weeks from Visit 5)

	Screening	Baseline	Implantation	Incision Healing Check	Activation (Follow up Clock Starts)	2 Month	3 Month: Primary Endpoint	4 Month
Demographics, screening exam, physical exam, & medical history	X							
Eligibility Determination	X	X						
Informed Consent	X							
3-day Voiding Diary Reminder Call		X				X	X	X
3-day Voiding Diary		X				X	X	X
OABq Assessment		X				X	X	X
Patient Satisfaction Survey		X				X	X	
End of Study Survey								X
Implant Procedure			X					
Incision Assessment				X				
Pictures Taken			X	X	X			

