Adverse Event (AE): Any untoward medical occurrence, unintended disease or injury, or untoward clinical signs (including abnormal laboratory findings) in subjects, users or other persons, whether or not related to the investigational medical device.

System and Procedure Related Adverse Event: Any adverse event related to the device or placement procedure. This can include risks associated with the procedure, implant site or stimulation such as infection, or related adverse events that occur in relation to implant placement, tibial nerve stimulation or device failure. The Sponsor maintains a list of expected adverse events and is responsible for determining anticipatedness.

Serious Adverse Event (SAE): A serious adverse event is any adverse event that results in death during the study period; is life-threatening; requires hospitalization or prolongation of existing hospitalization; results in persistent or significant disability or incapacity; results in a congenital anomaly or birth defect; requires medical or surgical intervention to preclude permanent impairment of a body function or to prevent permanent damage to a body structure, where the device is suspected to cause such intervention; other important medical events not captured by the other categories where the event may jeopardize the patient and may require medical or surgical intervention to prevent one of the other outcomes.

Unanticipated Adverse Device Effect (UADE): Unanticipated adverse device effect means any serious adverse effect on health or safety or any life-threatening problem or death caused by, or associated with, a device, if that effect, problem, or death was not previously identified in nature, severity, or degree of incidence in the investigational plan or application (including a supplementary plan or application), or any other unanticipated serious problem associated with a device that relates to the rights, safety, or welfare of the subject.

2-5-2 Classification of Events

2-5-2-1 Relationship to Device or Procedure

Related to study device: event has a reasonable possibility of a causal relationship to the device or tibial nerve stimulation and no other etiology explains the event.

Related to procedure: event has a reasonable possibility of a causal relationship to the procedure (device placement, removal, replacement) and no other etiology explains the event.

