AEs will be considered device or procedure related if they are classified as possibly, probably, or certainly related.

Assessment of certainty:

Certain: definitive evidence to suggest causal relationship, cannot be explained by other factors

Probable: evidence to suggest a causal relationship, the influence of other factors is unlikely

Possible: some evidence to suggest a causal relationship, but other factors may have contributed to the event

Unlikely: little evidence to suggest a causal relationship (e.g. the event did not occur within a reasonable time frame after therapy administration or procedure) or another reasonable explanation for the event

Not related: No evidence of any causal relationship with the trial intervention

2-5-2-2 Recording of Adverse Events

All AEs and categories of AEs (SAE's, UADE's, and AE's) will be captured and recorded in the case report forms (CRFs) which are used at each visit. Subjects will be requested to report adverse urologic events that are inconsistent with their normal medical condition that occur in between visits to the study coordinator or medical staff who will record on AE forms. Sites will be expected to follow related adverse events until resolution. All reported adverse events will need to be evaluated and assigned review to be coordinated by the Company:

- 1) Relatedness or causality to the study device

111-6133	Clinical Study Protocol ESSENCE	Rev: 1	Date Printed:4/10/2025	Page 23 of 38
----------	---------------------------------	--------	------------------------	---------------

2) Action taken

The Sponsor is responsible for determining if an adverse is a UADE.

At each contact with the subject, the Investigator will obtain information on AEs by specific questioning and examination. In the CRF for visits, if an event is reported, the AE checkbox will be selected. This selection will trigger a separate form to be filled out that records the following information:

1. Subject Number
2. Adverse Event (AE)
3. Date of AE onset
4. Date of AE cessation
5. Relationship to eCoin device
6. Relationship to eCoin procedure
7. Was the patient hospitalized? If yes, provide dates.
8. Will the patient continue with treatment, and will any be missed?
9. Did the patient add or change any other associated medication and what were the changes/additions?
10. Was any other action taken?

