When an AE has been recorded, the PI or sub-PI for the study must sign and approve the assessment on the Sponsor-provided CRF. The Study monitor will keep track of all reported AEs.

2-5-2-3 Device and Procedure Causality Assessment

The investigator or physician sub-investigator must indicate whether they believe the AE is unrelated, or related to the device, and make an assessment of certainty.

2-5-2-4 Reporting Procedures

Serious Adverse Events (SAEs) or suspected Unanticipated Adverse Device Effects (UADEs) must be reported to the sponsor within 48 hours of learning of the event. For suspected UADEs, the Sponsor will promptly provide an expectedness determination. Non-serious unexpected device related AEs must be reported via CRF to the sponsor within 7 days of subject reporting. The Investigator must promptly inform the Ethics Board or IRB of SAEs or determined UADEs per local reporting requirements.

These events will be reported by the Sponsor as appropriate to the regulatory authorities according to relevant jurisdictional medical device regulations. The Investigator will receive notification of these events across all study centers from the Sponsor.

As the eCoin device is a PMA-approved and commercially available device in the US, Medical Device Reporting requirements (21 CFR 803) are applicable to adverse incidents reported through this Study.

2-5-2-5 Adverse Event Reporting Period

All adverse events will be recorded from the time of signature of Informed Consent until a subject is exited from the trial. If the patient presents to the Investigator after the study period and a device-related AE is

suspected, the AE should be reported to the Sponsor via commercial complaint reporting. Complaints should be sent to [contact]

2-5-2-6 Medical Monitoring

This study will not use a Data Monitoring Committee. A Medical Advisor will review all adverse events and device deficiencies for consistent reporting.

2-5-3 Subject Withdrawal & Termination

This section describes reasons for withdrawal of subjects and termination of the study. A Statistical Analysis Plan (SAP) will describe in detail the methods for handling data from subjects who withdraw, or are withdrawn, early from the study.

2-5-3-1 Early Withdrawal of Subjects

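### Between visits the protocol asks subjects to report only urologic adverse events, although the key related events it names arise from a lower-leg implant; these may be captured late, up to 9 weeks after activation

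*Protocol*

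**What the plan says.** Protocol section 2-5-2-2 states that AEs of all categories go onto the CRFs used at each visit. For the time between visits it then says: "Subjects will be requested to report adverse urologic events that are inconsistent with their normal medical condition that occur in between visits". No other text in the protocol or SAP asks subjects to report events between visits. SAP section 11.1 says AEs are monitored continuously but gives no instruction to subjects.

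Other sections describe a wider range of events:

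- Section 1-5, on earlier experience with the device: "infection, stimulation discomfort, and migration are the key related adverse events".
- Section 1-3, on location: "The device is to be implanted under local anesthetic in the lower leg".
- Section 2-5-1, defining a system- or procedure-related AE: "This can include risks associated with the procedure, implant site or stimulation such as infection".
- Section 2-5-2-5 has AEs of every type recorded from consent until study exit.

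On timing, section 2-4-2 places the healing check at "Time: Between 9 and 19 days from Visit 3", activation at "Time: Between 23 and 43 days from Visit 3", and the 2-month visit at "Time: Between 7 and 9 weeks from Visit 5". SAP section 5.4 repeats these windows. Under section 2-5-2-4, SAEs and suspected UADEs "must be reported to the sponsor within 48 hours of learning of the event".

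**The concern.** A site that briefs subjects exactly as section 2-5-2-2 is written asks them to call about bladder problems. It does not ask them to call about a changed incision, a device that has moved or troublesome stimulation. Those are the events the protocol itself expects from this implant.

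Subjects may also hold back for other reasons. Section 2-4-10 tells them to expect tingling or a muscle twitch, so without an explicit request it is unclear when a sensation becomes reportable. Section 1-4-1 describes magnets for unwanted stimulation, so a subject could deal with discomfort without calling the site.

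Two things are at stake. One is prompt safety review. The study has no Data Monitoring Committee (section 2-5-2-6), so review depends on the sponsor and a Medical Advisor receiving reports. The other is the accuracy of the safety tables, which under protocol section 2-6-8 and SAP section 11.1 present related AEs by time point. Dates reconstructed weeks later are less reliable, and a mild event that has already resolved may not be recalled.

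**Working it through.** **Scope of the request against scope of the risks.**

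| Event type | Basis in the protocol | Covered by the between-visit request? |
|---|---|---|
| Urologic | 2-5-2-2 | Yes |
| Infection at the implant site | 1-5, 2-5-1 | No |
| Stimulation discomfort | 1-5, 2-5-1 | No |
| Device migration | 1-5 | No |

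**Time between scheduled visits.** The inputs are the windows in section 2-4-2. Healing check: days 9 to 19 after implant. Activation: days 23 to 43 after implant. The 2-, 3- and 4-month visits: weeks 7 to 9, 12 to 14 and 16 to 18 after activation.

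Shortest gap = earliest day of the later visit minus latest day of the earlier visit. Longest gap = latest day of the later visit minus earliest day of the earlier visit.

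| Interval | Shortest | Longest |
|---|---|---|
| Implant to healing check | 9 days | 19 days |
| Healing check to activation | 23 − 19 = 4 days | 43 − 9 = 34 days |
| Activation to 2 months | 7 × 7 = 49 days | 9 × 7 = 63 days |
| 2 to 3 months | (12 − 9) × 7 = 21 days | (14 − 7) × 7 = 49 days |
| 3 to 4 months | (16 − 14) × 7 = 14 days | (18 − 12) × 7 = 42 days |

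The longest gap, 63 days or 9 weeks, directly follows the start of stimulation.

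**The reminder call.** The only planned contact inside that gap is a telephone reminder by study staff about the diary, at least 3 days before the visit (section 2-4-9). No AE question is attached to it. If it were treated as a contact with AE questioning, a call at the minimum lead time would still leave 63 − 3 = 60 days.

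**Effect on the 48-hour clock.** The clock runs from when the site learns of the event. In the extreme case, an event begins just after activation and is first mentioned at a 2-month visit on the last permitted day. The sponsor could then hear of it up to 63 + 2 = 65 days after onset. This is an upper bound for an event that is serious or a suspected UADE and that nobody mentions earlier. It is not an expected delay.

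**Which risks the 9 weeks concerns.** Early incision infection is partly covered by the healing check and the activation visit, both with AE assessment and pictures. The 63-day interval bears mainly on discomfort, migration and late infection.

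**The case against.** The strongest reply is that the sentence makes one request and discourages nothing. Section 2-5-2-2 also requires the investigator to ask about AEs at each contact, and section 2-6-1 lists an Unplanned Visit CRF, so an unscheduled contact should bring out events of any kind. The AE form records onset and cessation dates, so an event that has resolved can still be entered later. Section 2-4-8 foresees a subject reporting uncomfortable stimulation, and section 2-4-7 provides for wound-care instruction and a review of study requirements before discharge. The consent template and labelling are attachments whose content is not available here, and they may carry a broader instruction. The all-AE recording rule is a duty of the site, so a narrower request to subjects does not strictly contradict it.

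Most of this stands, and it limits the point to late capture and possible recall loss. It does not explain why the one explicit request leaves out the protocol's own key events. A broader instruction in the consent form would still have to be reconciled with this sentence.

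A reader might be tempted to go further in three ways that the documents do not support:

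- **That leg and stimulation events would go unreported, or are asked about at scheduled visits alone.** The rule on questioning at each contact says otherwise.
- **That the 7-day reporting clock is also delayed for the three named risks.** Section 2-5-2-4 limits that clock to unexpected non-serious device-related events. Section 2-5-1 has the sponsor keep a list of expected events, and the named risks are presumably on it.
- **That each missed event shifts an arm's AE rate by 1/20, or 5 percentage points.** That division says nothing about how many events would be missed. SAP section 11.1 also counts events and subjects separately, so a missed event in a subject already counted leaves the overall subject percentage unchanged.

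**Conclusion.** The point holds as a reporting rule drawn too narrowly. Section 2-5-2-2 asks for urologic events between visits, while sections 1-5, 1-3 and 2-5-1 place the key risks at the implant and its stimulation, and section 2-5-2-5 intends every AE to be recorded.

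The size is a possible delay of up to 9 weeks between activation and the 2-month visit. With it come a correspondingly later start of the 48-hour clock for any serious event or suspected UADE, and possible loss of events that resolve in between. Related-AE counts could therefore be too low; the documents do not show that they would be.

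This assumes that sites brief subjects as the protocol is written, that no broader instruction stands in the consent form or labelling, and that subjects do not volunteer the event earlier. The change should be made because it improves safety detection at very little cost. The point does not call the efficacy analysis into question.

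**What to change.** In section 2-5-2-2, replace the restriction to urologic events, together with its qualifier about the subject's usual condition, with: *any adverse event, including urologic, implant-site and device-related events*. State that subjects receive this instruction at the implant visit and again at activation, in neutral wording that is identical in both arms. Check that the consent form and any subject handout say the same.

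The cost is one protocol sentence, the matching subject instruction, and a few more unscheduled calls and AE forms. There is also a small risk to blinding. The arms differ in whether stimulation is set at or below the level the subject feels, and site staff are blinded until the 3-month visit (protocol 2-4-8, SAP 5.3), so reports about stimulation could hint at the assignment. For that reason the wording should not single out felt or uncomfortable stimulation. A general request for any adverse event limits this risk but does not remove it.
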